3.2 Secondary Objectives

- a. To determine the prevalence and incidence of MRSA colonization of the nares, throat, perirectal, axilla, and groin areas among HIV infected patients and to study changes in the colonization rates over time.
- b. To determine the predictors of MRSA colonization and infection among HIV-infected persons including examination of demographics, sexual activity, hygienic practices, drug use, antibiotic and antiretroviral medications, sexually transmitted diseases, and HIV control.
- c. To evaluate the change in CD4 counts and HIV viral loads during the time of a MRSA or soft tissue infection.
- d. To characterize the molecular characteristics and the antimicrobial sensitivities of MRSA isolates in this population.
- e. To continue the previous retrospective study of MRSA infections among HIV-infected persons to examine the incidence of and describe the clinical features of MRSA infections and their response to treatment among HIV-infected patients seen within the HIV clinic at NMCSD. This study also will continue to compare those with and without MRSA infections in terms of demographic data, HIV viral loads, CD4 counts, and use of medications including antiretroviral and antimicrobial agents.

IV. BACKGROUND AND SIGNIFICANCE

MRSA was first recognized in 1961 and subsequently became a frequent cause of infections within the hospital setting. The first community-acquired MRSA infections occurred in the early 1980s. Within the past several years, the number of community-acquired MRSA cases has dramatically increased with incidence rates of 18 to 26 cases per

100,000 persons [1, 2]. In addition to individual cases, numerous outbreaks have occurred among prison inmates, athletes, military trainees, and men who have sex with men (MSM) [14-18].

Patients presenting with community-acquired MRSA infections typically present with skin or soft tissue infections such as folliculitis, furuncles, carbuncles, abscesses, or cellulitis [1, 7]. Despite that most of these infections occur in young, otherwise healthy individuals, community-acquired MRSA infections have led to a high hospitalization rate with up to 25% requiring admission for the management of the MRSA infection [1].

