5.1 General Approach

This is a prospective, randomized, double-blind study examining the incidence and risk factors for MRSA colonization and infection among HIV-infected persons and the efficacy of decolonization procedures of mupirocin (Bactroban®) nasal ointment and hexachlorophene (pHisoHex®) soaps compared to a placebo nasal ointment and body soap. Inclusion criteria include adult (≥ 18 years) HIV-positive patients; exclusion criteria include the presence of a known allergy to mupirocin (Bactroban®) nasal ointment or hexachlorophene (pHisoHex®) soaps, pregnant or breastfeeding females, age < 18 years, persons who are healthcare providers with direct patient contact, and inability to participate in study for its two year duration. A history of MRSA infection or colonization is not an exclusion criterion for this study. Patients will be offered enrollment into the study at the time of presentation to the HIV clinic for routine care by their primary care physician and/or a study investigator. General Institutional Review Board (IRB) approved advertisement posters about the study will be posted in each clinic.

After signing the informed consent which includes a HIPAA form, the patient will be registered with the Data Coordination Center (DCC) and receive a participant identification number (PIN). A patient will be assigned a PIN centrally once the patient agrees to participate in a Infectious Disease Clinical Research Program (IDCRP) study. If a patient agrees to participate in other IDCRP studies, this same PIN will be used to link that patient to these other studies. The patient will also be assigned a subject identification number unique to the patient and this study.

Patients will then undergo swabs for determining colonization of MRSA and will fill out a questionnaire containing data regarding demographics, sexual activities,

substance use, medication use, history of soft tissue infections, and potential risk factors for MRSA. Study coordinators will review the patient's medical record for data regarding medical history. Patients will have repeated swabs, questionnaires, and review of their medical records every six months (+/- 2 months) during the two year study enrollment.

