6.3 Active Surveillance & Clinic Assessments

Each study participant will be seen a minimum of five times over the 24-month study period by a study physician or study team member at the clinic (baseline visit and every six months (+/- 2 months) for a two year period). The maximum number of visits depends on if the patient has repeated infections or colonization for MRSA; this will likely not exceed 12 visits during the 2 year study period. This includes Visit 1 to sign the informed consent and register subject with DCC (assigned a PIN). Women of childbearing age will undergo a urine pregnancy test to assure that she meets inclusion/exclusion criteria. Enrolled patients will fill out questionnaires including data on prior MRSA or soft tissue infections, recent hospitalizations, demographic information (age, race, sex), substance use (alcohol, tobacco and illicit drugs), current and recent (within the past 12 months) antibiotics, current receipt of highly active antiretroviral therapy (HAART), contact with persons with a history of soft tissue infections and/or MRSA, relative or contact who works in the healthcare setting, exercise habits, sexual activities, sexually transmitted diseases, and activities previously associated with MRSA including sports, use of public baths/saunas, and hygienic practices (refer to case report forms). Each participant will have swabs of their nares, throat, axilla, groin, and perirectal area obtained for determining MRSA or MSSA colonization. Study coordinators will examine the patient's medical records and the hospital computer database for medication use, medical conditions including MRSA or soft tissue infections, hospitalizations, sexually transmitted diseases, and HIV data including CD4 count, HIV viral loads, and CDC staging.

During regular study visits 2, 3, 4, and 5, patients will have repeated swabs, questionnaires and review of their medical record which occurs every six months (+/- 2 months). The study duration for each participant is 24 months.

Patients will have the following swabs to detect colonization of MRSA or MSSA performed:

[figure not shown]
- one swab of both nares;
- one swab of the throat
- one swab of the bilateral groin areas;
- one swab of the axilla areas; and
- one swab of the perirectal area.

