Patients will be evaluated at 6, 12, 18, and 24 study months (\pm 2 months) for repeat swabs (1. one swab of both nares; 2. one swab of the throat; 3. one swab of the bilateral groin areas; 4. one swab of the axilla areas; and 5. one swab of the perirectal area). Patients will also complete questionnaires regarding recent antibiotic use, recent soft tissue infections, recent sexually transmitted diseases, hospitalizations, substance use, sexual activities, and activities previously associated with MRSA (refer to case report forms). Study coordinators will search the patient's medical records and the hospital computer database for medication use, medical conditions including MRSA or soft tissue infections, hospitalizations, sexually transmitted diseases, and HIV data including CD4 count, viral loads, and CDC staging.

Culture results regarding MRSA carriage are to be finalized within 3-4 days of collection. Patients found to have a positive culture for MRSA during the study period from the colonization swabs will be randomized in a 1:1 double-blinded fashion to mupirocin (Bactroban®) nasal ointment twice daily for seven days plus hexachlorophene (pHisoHex®) washes with showering once daily for seven days or to a placebo nasal ointment (white petroleum) and a placebo body soap with no antimicrobial activity for seven days. The patient will be randomized within 7 days of the receipt of the MRSA positive culture result. Women of childbearing age will have a urine pregnancy test to assure they are not pregnant before dispensing of these medications; women found to have a positive pregnancy will be terminated from the study.

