Patients will be asked to report to their enrolling HIV clinic for any soft tissue infections or any infection thought to be secondary to MRSA; if able, cultures of the wound site will be obtained. Blood cultures will be obtained at the primary provider's discretion depending on the presence of fevers, toxemia, and the extent of soft tissue involvement. Patients will also have repeated screening for colonization including nares, throat, groin, axilla, and perirectal swabs (5 total swabs) at this time. CD4 counts and an HIV viral load will be obtained at the time of the soft tissue infection or with any MRSA infection for patients presenting to the enrolling site. Patients with positive wound culture and/or blood cultures for MRSA will be classified as a "MRSA infection." Those with a soft tissue infection without positive cultures from these sites will be classified as a "Soft Tissue Infection NOS." The patient will be treated with intravenous or oral antibiotics and/or surgical procedures at the discretion of the medical provider that the patient presents to for evaluation. Patients who have an infection while located remotely from the HIV clinic will be given a contact information card and will be asked to call the site PI or study coordinator at their enrolling site to notify them of the infection. The site PI or study coordinator will try to arrange for the aforementioned tests to be performed at the local medical clinic; CD4 counts and HIV viral loads will not be performed for patients presenting remotely to the enrolling site. In addition, coordinators will gather information on the tests and treatments performed. Patient questionnaires will be completed for patients experiencing a soft tissue infection or MRSA infection (refer to case report forms).

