will be reported to the study lead PI using this unique identifier, together with a SAMMC-assigned identifier. These data will be utilized to characterize the MRSA isolates colonizing and infecting HIV patients, understanding the relationship between colonizing and infection-related isolates, and to determine if HIV patients acquire new strains or remain colonized with the same strain over time.

The primary endpoint of the study is the effectiveness of decolonization procedures with application hexachlorophene (pHisoHex®) soaps and nasal mupirocin (Bactroban®) compared to placebo among patients found to be colonized with MRSA in the prevention of future colonization with MRSA. As a secondary part of the study's objectives, we will also examine the effectiveness of these decolonization procedures on infections with MRSA and on soft tissue infections.

The following assessments will be performed:

a. Clinical (Visits 1, 2, 3, 4, 5, unscheduled visits)

1. Informed Consent (visit 1 only)
2. Patient Questionnaires regarding medical history, medication use, and potential risk factors for MRSA
3. Demographics (visit 1 only)
4. Review of patients medical record by study coordinators
5. Study medication dispensing (unscheduled visits for positive MRSA colonization only)
6. Adverse event review (unscheduled visits in which patient receives a study medication only)
7. Medication adherence questionnaire (visit following decolonization therapy)

b. Laboratory Values (Visits 1, 2, 3, 4, 5, unscheduled visits)

1. Swabs for MRSA colonization of the nares, throat, groin, axilla, and perirectal areas (5 swabs)
2. Pregnancy test (visit 1; visits for MRSA colonization before decolonization medications are prescribed for women of childbearing age)
3. CD4 count and HIV viral load (MRSA or soft tissue infection visit only)
4. Blood cultures (two sets) at the physician's discretion (MRSA or soft tissue infection visit only)
5. Wound culture (MRSA or soft tissue infection visit only)

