- (2) Is the treatment effect different for repeat administrations of hexachlorophene/mupirocin? The rate of MRSA positive versus negative for recolonization reoccurrence through the sequence 1 versus 2 versus 3 versus 4 treatments will be assessed by a test of trend.
- (3) Is there a persistent or repeated-treatment effect? The overall rates of MRSA recolonization at 6, 12, 18, and 24 months will be assessed by a test of trend.
- (4) Is there an individual propensity for susceptibility and what are the treatment differences between placebo and hexachlorophene/mupirocin in terms of length of time for being negative for MRSA colonization on repeated testing? A Kaplan-Meier long-rank test will be conducted on three groups: initially negative, initially positive treated with hexachlorophene/mupirocin, and initially positive treated with placebo, where survival is defined as not having acquired MRSA.

For the secondary objectives, part (a) will be assessments of the rates in which prevalence is defined as the number of patients colonized with MRSA at the beginning of

the study divided by the total population studied, and the incidence as the number of new infections per calendar time divided by the total population studied. For objective (b) examining for predictors of MRSA, we will create a multivariate logistic regression model and use a backward stepwise approach. For part (c), to evaluate if there is a significant change in the CD4 count and/or viral load pre- versus during a MRSA infection we will utilize a 1-way ANOVA. We will also compare pre-MRSA infection with after MRSA resolution as well as the counts during the infection with those after resolution. Finally, objective (d) will be a descriptive analysis of the molecular and microbiologic characteristics of the isolates. The main statistical data from the retrospective chart review study of HIV patients at NMCSD will be presented by descriptive analyses. We will compare demographics and HIV clinical data between those with and without MRSA using rank sum tests and Fisher's exact tests depending on the variable characteristics (categorical or continuous). A multivariate logistic regression model for predictors of MRSA will then be developed using a backward stepwise approach using Stata software.

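### Objective (c) compares CD4 and viral load before, during and after infection, but the study samples only at the infection visit and the planned analysis leaves out timing, HAART changes and within-patient pairing

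*Combined protocol and SAP*

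**What the plan says.** Section 3.2 gives objective (c) as "To evaluate the change in CD4 counts and HIV viral loads during the time of a MRSA or soft tissue infection". Section 6.6 goes further and promises to assess the effect of MRSA infection on both markers.

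Section VII names a test for the first comparison only: "pre- versus during a MRSA infection we will utilize a 1-way ANOVA". It then adds two comparisons without a method: "We will also compare pre-MRSA infection with after MRSA resolution as well as the counts during the infection with those after resolution".

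The sampling is narrower than the analysis. The laboratory list in Section 6.3 has "CD4 count and HIV viral load (MRSA or soft tissue infection visit only", and the schedule in Appendix D marks CD4 and viral load in the infection-visit column alone. Section 6.3 also says that "CD4 counts and HIV viral loads will not be performed for patients presenting remotely to the enrolling site".

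Other values are abstracted by coordinators from the medical record and hospital database. Section 6.3 lists "HIV data including CD4 count, HIV viral loads, and CDC staging" at enrolment and "HIV data including CD4 count, viral loads, and CDC staging" at months 6, 12, 18 and 24. Section 5.1 sets the frequency: "review of their medical records every six months (+/- 2 months) during the two year study enrollment".

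Treatment data are collected. Section 6.3 asks about HAART at enrolment and has medication use searched at each later review. Appendix D also places a questionnaire covering medications at the infection visit.

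**The concern.** Three time points are to be compared and the study samples one of them. Nothing says how old a before value may be, how late an after value may be, or what counts as resolution. An analyst would have to choose among charted values after seeing them.

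HAART moves both markers in its own right. If it is started between the infection visit and the after value, the CD4 rise looks like recovery from infection. If it is started between the before value and the infection visit, it can hide a fall due to infection. The protocol's own background adds a problem of direction: Section IV lists low current CD4 and high viral load as risk factors for MRSA, so a fall from before to during may precede the infection rather than follow it.

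At stake is whether objective (c) can say anything about infection, as Section 6.6 intends. The randomized comparison is not touched.

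**Working it through.** The documents give no sample size, effect size or standard deviation for objective (c), so there is no stated figure to reproduce. The check sets the sampling against the analysis and adds supporting arithmetic.

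**1. Which time points have a study sample?**

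| Time point | Study draw | Other source described |
|---|---|---|
| Before | None | Record review; by chance an earlier infection visit; possibly linked study data |
| During, at the enrolling site | Yes | Record review |
| During, remote | None | Only if the record holds a result |
| After | None; no resolution visit | Record review; by chance a later infection visit; possibly linked study data |

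Section 10.3 says that blood is destroyed after testing, so a missing value cannot be recovered from storage.

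**2. How far apart are the record reviews?** The visit windows are 6 ± 2 = 4 to 8 months and 12 ± 2 = 10 to 14 months, and so on.
- Baseline to Visit 2: 4 to 8 months.
- Consecutive later visits: shortest 10 − 8 = 2 months, longest 14 − 4 = 10 months.

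These are review dates. The laboratory results abstracted at them have no stated window relative to an infection.

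**3. How many MRSA infections?** Section VII cites 13 per 1000 person-years from one cohort and 40 per 1000 persons in 2005 at one of the sites. Expected number = participants × 2 years × rate.
- 500 participants: 500 × 2 × 0.013 = 13; 500 × 2 × 0.040 = 40.
- 550 participants: 550 × 2 × 0.013 = 14.3; 550 × 2 × 0.040 = 44.

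The range is about 13 to 44. Fewer will have a study draw, because remote patients have none. Soft tissue infections, which objective (c) includes but the ANOVA sentence does not mention, would add events.

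**4. What does ignoring the pairing do?** With within-patient correlation ρ, the variance of the before-during mean difference is 2σ²(1 − ρ)/n, while a 1-way ANOVA that treats the values as independent uses 2σ²/n. Its standard error is too large by 1/√(1 − ρ): 1.41 at ρ = 0.5, 1.83 at 0.7 and 3.16 at 0.9. In a simulation with three time points, 40 patients and no true change (5,000 runs), the nominal 5% test rejected in 0.26%, 0.06% and 0% of runs. These correlations are assumed. The pairing fault on its own therefore masks a change rather than creating one.

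**5. What could HAART changes do?** This is an illustration only; none of its inputs is in the documents. Suppose 10 to 30% of patients start or change HAART before the after value and gain 50 to 150 cells/mm³, with a standard deviation of within-patient change of 100. The mean shift with no infection effect is 0.10 × 50 = 5 up to 0.30 × 150 = 45 cells/mm³. An unadjusted paired t-test at a nominal 5% then rejects in 5% to 22% of 20,000 simulated runs with 13 infections, and in 6% to 63% with 40. This is not the named ANOVA; it shows what a plausible choice for the unspecified after comparisons could do.

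**The case against.** The fair defence is that this is brevity. Section VII gives objective (c) a few lines, it is secondary, and saying nothing about windows or HAART is not a decision to ignore them. Treatment data are collected, including at the infection visit, so an analyst could adjust. That stands in part: the data exist and the remedy is cheap. It does not rescue the one method that is named, which uses neither timing nor HAART nor pairing.

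Several stronger readings are tempting, and the documents do not support them.
- A reader might infer that the before and after values can only be routine-care results. Section VII names no source. Sections 5.1 and IX link participants to other studies through a common identifier, and a second infection visit could supply a value. Record review is the only systematic route described, which is a weaker statement.
- A reader might infer that the charted results are undated. The case report forms are not supplied. What is shown is that no window is stated.
- A reader might take 40 to 44 infections as a ceiling. That figure rests on one site's rate in one year, the other cited rate gives 13 to 14, and soft tissue infections come on top.
- A reader might conclude that the main analysis should be limited to infections without a HAART change. A low CD4 count at the infection visit may itself prompt a change, so that restriction could selectively remove the patients with the largest falls.

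**Conclusion.** The concern holds as a weakness in the analysis of a secondary objective. Following Section VII as written would mix background drift and HAART changes with any effect of infection, in either direction, and the ANOVA would also waste the pairing. About 13 to 44 MRSA infections are expected over two years, assuming that the cited rates apply and that 500 to 550 participants are followed throughout; soft tissue infections are additional.

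The size of the bias cannot be derived from the documents. A reader might take the 5 to 45 cell shift or the rejection rates above as an estimate; they only show a range under assumed inputs. That the before and after values are mainly charted is an inference from the schedule, though a strong one. The primary comparison of decolonization with placebo is unaffected, so this is a worthwhile improvement rather than a critical fault.

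**What to change.** In Section VII, for objective (c):
1. Replace the 1-way ANOVA with a within-patient model (paired or mixed) for all three comparisons, including sample timing and HAART status at each sample, from data already collected.
2. As a reference, compute the change over infection-free intervals of similar length from charted values already under review.
3. Report infections with no HAART start, stop or change between samples as a sensitivity analysis.
4. State in advance the windows for before and after values and the definition of resolution. The documents give no basis for particular lengths, so the sponsor should choose and justify them before the values are examined.
5. Say whether soft tissue infections are included, since Section 3.2 and Section VII differ, and how remotely treated infections contribute.
6. Describe the result as an association, and align Section 6.6 with that. Even with HAART in the model, a change prompted by the infection lies downstream of it.

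The cost is recording sample dates if the forms do not already capture them, somewhat more analysis work, and fewer evaluable infections once windows apply. That loss is real when the starting number may be as low as 13. No extra blood draw or visit is needed.

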HIV infection is a known risk factor for both MRSA colonization and infection [7, 8, 11]. A recent study showed that community-acquired MRSA increased six-fold among HIV-infected persons during the years 2000 to 2003 [7]. Risk factors for community-acquired MRSA among HIV-infected patients cited in the literature include a history of MSM or intravenous drug use as the patient's HIV transmission risk factor, a low current CD4 count, high HIV viral load, and the absence of trimethoprim-sulfamethoxazole (TMP/SMX) prophylaxis [7]. Other studies found an association with exposure to public hot tubs/saunas, having a sex partner with a skin infection, and prior beta-lactam

antibiotics [13, 25]. Colonization with MRSA among HIV infected persons has been linked to low CD4 count (<100 cells/mm³), lack of TMP/SMX prophylaxis, recent antibiotic use, and hospitalizations [26, 27].

A retrospective case-control study was performed including the years of 1993-2005 among 425 HIV patients seen at the Naval Medical Center San Diego (NMCSD), of whom, 25 (5.9%) patients were found to be infected with community-acquired MRSA. All cases occurred after 2002, with a 17-fold increase from 2003 to 2005 (Chi-square test of trend 15.7, p<0.001). The annual incidence during the year 2005 among our HIV patients was 40 cases/1000 person-years compared to 2.28 cases/1000 person-years (or 741 cases/325,000) among HIV-negative persons (18-fold higher rate). In the univariate analyses, lower current CD4 count, CDC stage C vs. A, history of syphilis, and exposure to beta-lactam antibiotics in the past year were predictive of MRSA. In the multivariate model, history of syphilis and exposure to beta-lactam antibiotics remained as significant predictors [12].

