We also propose to continue to review the charts (IDCRP-049) of all HIV-infected patients within the HIV clinic at NMCSD. We will review all patients' demographics, CDC stage, current CD4 counts, CD4 nadir, current HIV viral loads and medication use including antiretroviral and antimicrobial medications. We will also identify those patients who were diagnosed with MRSA infection during the time they were infected with HIV. Patients charts in the HIV clinic will be reviewed from 1 January 1993 (the beginning of CHCS) or the date of HIV positivity (whichever is later) through 1 March 2011 in an ongoing fashion. Among patients with MRSA, the following data will be collected from the charts and from CHCS: age, sex, race, years of HIV infection, CDC stage, CD4 count nadir, CD4 current value, current HIV viral load, medication use including antiretroviral and antimicrobial medications, antibiotics for MRSA, time of MRSA infection, type of MRSA infection, CD4 and viral load counts around the time of MRSA diagnosis, type of treatment, whether or not they were hospitalized and for how long, duration of the MRSA infection, any MRSA relapses, risk factors for MRSA, HSV2 serology, RPR serology,

GC/Chlamydia testing, and any antibiotics used during the previous two years. Data will be entered into a Microsoft Excel file without personal identifiers for analyses. Datasets from the prospective RV210 study and this retrospective study will be maintained in separate databases since study populations will be diverse, however linkage between datasets will be possible through linking identifiers.

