5.2 Subject Population

The study population will consist of those volunteers from the HIV clinics at the participating military HIV treatment centers including NMCSD, WRNMMC, SAMHS, and NMCP in their respective catchment areas. Each clinic has approximately 500 HIV-positive patients at any one time. Since all adult HIV patients are eligible who do not have allergies to the agents utilized in this study (mupirocin (Bactroban®) nasal ointment or hexachlorophene (pHisoHex®) soaps), who are not healthcare workers with direct patient contact, and who are not pregnant or breastfeeding, over 95% of clinic patients will be eligible for enrollment. A history of prior MRSA colonization and/or infection does not exclude entry into this study. The total population of the study will be 550 participants. If approximately 10-15% of participants carry the bacteria MRSA, then approximately 38 patients will receive topical antibacterial treatment and the other 38 will receive placebo. Enrollment will be on a continuous basis until 550 participants have been enrolled. The number of subjects per site will vary. The San Antonio Military Medical Center will only enroll patients that reside locally to their medical treatment facility. For the retrospective cohort, the study population will consist of all HIV patients who are 18 years or older and followed in the NMCSD HIV clinic.

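### The chart-review predictor model (secondary objective e) specifies no adjustment for time at risk or calendar period, so factors tied to length of follow-up or era can be selected as MRSA predictors with no true effect

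*Combined protocol and SAP*

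**What the plan says.** Section 3.2, objective (e), continues an earlier retrospective study at NMCSD. It asks for the incidence of MRSA infection and for a comparison of patients with and without it.

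- **Population (Section 5.2):** "the study population will consist of all HIV patients who are 18 years or older and followed in the NMCSD HIV clinic". No sampling or matching of controls is described.
- **Observation window (Section 5.1):** charts are read from 1 January 1993 "or the date of HIV positivity (whichever is later) through 1 March 2011 in an ongoing fashion".
- **Analysis (Section VII):** "We will compare demographics and HIV clinical data between those with and without MRSA using rank sum tests and Fisher's exact tests", and then "A multivariate logistic regression model for predictors of MRSA will then be developed using a backward stepwise approach using Stata software". No person-time offset, censoring rule, time-to-event model or calendar term is given.
- **Data items (Section 5.1):** the list for all patients covers demographics, CDC stage, CD4 (current and nadir), viral load and medication. Years of HIV infection and the time of MRSA infection are listed only for patients with MRSA. Date of last contact is not listed.
- **Calendar trend in the same clinic (Section IV):** "All cases occurred after 2002, with a 17-fold increase from 2003 to 2005". For 2005: "The annual incidence during the year 2005 among our HIV patients was 40 cases/1000 person-years compared to 2.28 cases/1000 person-years" in HIV-negative persons.

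**The concern.** A logistic model of MRSA yes/no treats every patient as having had the same opportunity to become a case. Here the opportunity differs in two ways. Patients enter at different dates, so their time at risk ranges from near zero to about 18 years. And the rate itself moved from none through 2002 to 40/1000 person-years in 2005. A patient diagnosed in 2009 had little more than two years in which to become a case; one already in care in 2003 had about eight.

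Length of follow-up and era are therefore confounders. Any characteristic associated with them (cumulative medication exposure or CD4 nadir are plausible examples) can differ between cases and non-cases without affecting the MRSA rate. Backward selection can then retain it as a predictor. The rank sum and Fisher comparisons have the same weakness. At stake is the list of predictors that Section IV hopes will inform future preventive strategies.

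**Working it through.** **1. The protocol's own figures (Section IV) reproduce.** 25/425 = 5.88%, stated as 5.9%. 741/325,000 = 2.28/1000. 40/2.28 = 17.5, stated as 18-fold. No sample size or event target is given for the retrospective model.

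**2. Rates used, per 1000 person-years.**

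- Through 2002: 0 (Section IV).
- 2005: 40 (Section IV).
- 2003: 40/17 = 2.35, reading the 17-fold rise as a ratio of rates.
- 2004: assumed, the geometric mean √(2.35 × 40) = 9.70.
- After 2005: assumed, 10 to 40. The documents give no figure.

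**3. Risk of ever having MRSA for otherwise identical patients, all followed to 1 March 2011.** Risk = 1 − exp(−H), where H is the sum over calendar years of rate × years observed. From 2003 to 2005, H = (2.35 + 9.70 + 40)/1000 = 0.0521. From 2006 to 1 March 2011 is 5.16 years; from 2009 it is 2.16 years.

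| Entry | Years at risk | H at 10/1000 | Risk | H at 40/1000 | Risk |
|---|---|---|---|---|---|
| 2003 | 8.16 | 0.0521 + 0.0516 = 0.1037 | 9.85% | 0.0521 + 0.2065 = 0.2585 | 22.8% |
| 2009 | 2.16 | 0.0216 | 2.14% | 0.0865 | 8.28% |

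Odds ratio, 2003 v 2009 entry:

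- at 10/1000: (0.0985/0.9015)/(0.0214/0.9786) = 5.0;
- at 40/1000: (0.2278/0.7722)/(0.0828/0.9172) = 3.3.

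Nobody in this example left before 2003, and the patients differ only in when observation began.

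**4. What reaches a null marker.** Suppose the two entry groups are equal in size and a marker with no effect is present in 65% of the 2003 group and 35% of the 2009 group (all assumed).

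- At 10/1000: risk with the marker is 0.65 × 0.0985 + 0.35 × 0.0214 = 0.0715; without it, 0.35 × 0.0985 + 0.65 × 0.0214 = 0.0484. Odds ratio 1.5.
- At 40/1000: 0.65 × 0.2278 + 0.35 × 0.0828 = 0.1771; without it, 0.35 × 0.2278 + 0.65 × 0.0828 = 0.1336. Odds ratio 1.4.

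With equal marker prevalence in both groups the two risks are the same and the odds ratio is 1.

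**5. Why both person-time and calendar period are needed.** Dividing by person-time, the 2003 entrants have 0.1037/8.16 = 12.7/1000 against 10/1000 for the 2009 entrants (ratio 1.27), or 0.2585/8.16 = 31.7 against 40 (ratio 0.79). Person-time removes most of the distortion. The rest is the calendar trend, and its direction depends on what happened after 2005.

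**The case against.** The strongest reply has five parts.

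- **Patients who left before 2003 may not exist in this cohort.** If the 17-fold rise is in case counts, only 1 to 17 fits, because 2 to 34 would exceed the 25 cases. Then 17/0.040 = 425 person-years, which is the whole cohort under observation in 2005. That looks like an active clinic roster with look-back. The step is an inference, since 425 may simply have been used as a head count, but it stands as a warning. A reader might infer large odds ratios from a substantial group with no chance of becoming a case. The documents give no such share, so no figure here uses one. Unequal time at risk among patients diagnosed between 2003 and 2011 remains on either reading.
- **The plan does not rule out adjustment.** True: it lists no final covariates, and the date of HIV positivity must be known for everyone because it sets the window. But no adjustment is specified, and last contact is not collected for non-cases.
- **The earlier work is called case-control.** Logistic regression can serve there if controls are sampled by time at risk. This plan uses the whole clinic and describes no such sampling.
- **The earlier predictors do not look like follow-up artefacts.** Section IV reports lower current CD4, CDC stage C, syphilis history and past-year beta-lactam exposure, the last already confined to one year. This stands against predicting any particular false finding. It does not show that the method is sound for data to 2011.
- **The results are called descriptive.** Section VII nevertheless goes on to tests and a predictor model.

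**Conclusion.** The point holds, limited to secondary objective (e). With no adjustment specified for time at risk or calendar period, a factor correlated with length of follow-up or era can be selected as an MRSA predictor with no true effect.

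That time at risk is unequal and that the rate rose steeply from zero come from the documents. The size does not. The 3.3–5.0 for entry year and the 1.4–1.5 for a null marker rest on the interpolated 2004 rate, the assumed 10–40/1000 after 2005 and follow-up of everyone to 1 March 2011. The second pair also rests on the assumed 65% v 35% split and equal groups.

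Three stronger readings are not supported. Follow-up time and calendar period would not themselves emerge as spurious risk factors; they are omitted confounders. Not every predictor is biased, because one unrelated to follow-up and era is not affected. And the randomised comparison does not use this model, so it is untouched.

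**What to change.** 1. Record for every patient, case or not: cohort entry date, last clinic contact and date of first MRSA infection.
2. Report MRSA incidence per person-year by calendar period, as Section IV already does for 2005.
3. Replace the logistic model with a Poisson model (log person-time offset) or a Cox model. Person-time runs from the later of 1 January 2003 or cohort entry to the earliest of first MRSA, last contact or 1 March 2011. Adjust for calendar period; a Cox model with calendar date as the time axis and delayed entry does this directly.
4. Use covariate values that precede the event where the charts already give them. For non-cases, state the date to which a current value refers.
5. Present the rank sum and Fisher comparisons as description only.

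The cost is modest: some extra date abstraction for non-cases from charts already under review, and slightly more analysis work. Fully time-updated CD4, viral load and drug data would be substantial new abstraction over up to 18 years, so it should be optional.
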